10. PROTOCOL DEVIATIONS/VIOLATIONS

Deviations and violations from the protocol will be recorded appropriately. Protocol deviations will be classified into, but not necessarily limited to, the following categories:

- Excluded concomitant medication
- Informed consent
- Other/GCP issue
- Randomization procedure
- Selection criteria not met (i.e., violation of inclusion/exclusion criteria)
- Serious adverse event reporting
- Study procedure
- Treatment deviation
- Visit scheduling

Classification of deviations as major protocol deviations/violations and decisions regarding exclusion of patients from the PP will be decided on a case-by-case basis without knowledge of the treatment assigned and before database lock or Cohort 1 unblinding. Major protocol deviations will be presented in a summary table by protocol deviation category. All protocol deviations will be listed. Major protocol deviations that exclude patients from the PP population will be summarized separately.

Besides the listing for patients excluded from the PP population with reason as specified in Section 5.2, a separate listing will be created for patients who have met TFR during IP and thus excluded from PP population. This listing will include the date and study day of their first occurrence of confirmed TFR, and relevant description (e.g., medication name, indication, dose/frequency, Baseline dose/frequency, duration of use, or medical procedure name). This listing will also include the date and study day of their first IP dose, and the date and study day of their W10 endoscopy (if available). This listing will be reviewed, confirmed, and finalized before database lock or Cohort 1 unblinding. See detail about treatment failure rules data review in [Appendix 1.3](#).

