13.9. Treatment Failure Rules

Treatment failure rules (TFR) will be applied to the primary analyses of all efficacy endpoints. Patients will be considered to have failed treatment if any of the following occur:

- Any protocol-prohibited change in medications including:
 - Post-Baseline initiation of, or increase in total daily dose level higher than the maximum dose taken between the Screening and Baseline visits in:
 - Corticosteroids or 5-ASA dose to treat UC
 - Prolonged course of systemic corticosteroids > 14 days for treatment of disease other than UC
 - Initiation of an immune suppressing therapy including 6-mercaptopurine (6-MP), azathioprine, anti-TNF agents, vedolizumab or tofacitinib
- A colectomy (partial or total) or an ostomy

[REDACTED]

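### The Per-Protocol set drops patients who met the treatment failure rules, so it selects on outcome and a PP-ITT difference does not isolate protocol deviations

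*SAP*

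**What the plan says.** Protocol 13.9 makes TFR part of the efficacy outcome: "Treatment failure rules (TFR) will be applied to the primary analyses of all efficacy endpoints", and "Patients will be considered to have failed treatment if any of the following occur". The list has two main items.

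- The first is headed "Any protocol-prohibited change in medications including". It covers a post-Baseline start or increase of "Corticosteroids or 5-ASA dose to treat UC", the start of an immune-suppressing therapy (thiopurines, anti-TNF agents, vedolizumab or tofacitinib among them), and one component that is not about UC: "Prolonged course of systemic corticosteroids > 14 days for treatment of disease other than UC".
- The second stands apart from the medication item: "A colectomy (partial or total) or an ostomy".

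SAP 6.1.1 and 6.2.2 apply this in ITT. A patient who meets TFR before the Week 10 evaluation is set to non-responder by non-responder imputation (NRI), for remission and for all key secondary endpoints.

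SAP 5.2 gives the purpose of PP: to show how far major protocol violators and deviators influence the primary results, for clinical remission (sensitivity analysis) and clinical response (additional analysis). Its visible exclusions based on concomitant medication concern use for conditions other than UC. SAP Table 2 specifies NRI for the PP analysis of remission.

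SAP 10 then provides for a separate listing of "patients who have met TFR during IP and thus excluded from PP population".

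**The concern.** One post-randomization event is handled in two ways. In ITT it is a failed outcome; in PP it removes the patient. Starting or raising corticosteroids for UC, starting a biologic, or having a colectomy will mostly happen because treatment has not worked. Removing these patients is therefore not the same as removing patients who took the wrong drug or were ineligible.

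What is at stake is how the PP result can be read. If PP and ITT differ, the reader should be able to attribute the gap to non-adherence. Under SAP 10 part of the gap comes from deleting failures, and the two parts cannot be separated. If PP and ITT agree, that is also less informative, because the two influences may have cancelled.

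**Working it through.** **Inputs.** Planned Week 10 remission of 16% on RPC1063 and 6% on placebo, with 400 and 200 patients (Protocol 13.1). Neither document gives a TFR rate, so every TFR rate below is an assumption. An adult placebo response rate is not given either, so only remission is quantified; the mechanism is the same for response.

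**Plan's own figure.** Protocol 13.1 states at least 90% power for 16% versus 6%, 400 versus 200, two-sided Fisher's exact test at 0.05. Exact enumeration gives 96.0%, which agrees. This figure is not in dispute; it is the starting point.

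**Formula.** Let p be an arm's ITT remission rate and f its TFR fraction. TFR patients are all non-remitters under NRI, so removing them leaves the numerator unchanged and shrinks the denominator:

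PP rate = p / (1 − f); rise = p·f / (1 − f)

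This takes TFR as met before the Week 10 evaluation and no other PP exclusions.

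**Example.** At 5%/10%: active 64/380 = 16.84%; placebo 12/180 = 6.67%; difference 10.18 points; odds ratio (64/316)/(12/168) = 2.84.

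| TFR active/placebo | Active | Placebo | Difference (points) | Odds ratio | Power |
|---|---|---|---|---|---|
| TFR patients kept (as ITT) | 16.0% | 6.0% | 10.0 | 2.98 | 96.0% |
| 5%/5% | 16.8% | 6.3% | 10.5 | 3.00 | 96.0% |
| 10%/10% | 17.8% | 6.7% | 11.1 | 3.03 | 96.1% |
| 5%/10% | 16.8% | 6.7% | 10.2 | 2.84 | 93.6% |
| 5%/15% | 16.8% | 7.1% | 9.8 | 2.67 | 89.7% |
| 5%/20% | 16.8% | 7.5% | 9.3 | 2.50 | 83.8% |
| 10%/5% | 17.8% | 6.3% | 11.5 | 3.21 | 97.8% |

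The power column treats the reduced arm sizes as fixed and is approximate.

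**Direction.** Placebo rises by more than active only if 0.06·f_P/(1 − f_P) > 0.16·f_A/(1 − f_A). That means the odds of TFR on placebo must exceed 16/6 = 2.67 times those on active. At 5%/10% the ratio is (0.10/0.90)/(0.05/0.95) = 2.11, so the difference grows although placebo has twice the failures. At 5%/15% it is 3.35 and the difference shrinks.

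The odds ratio turns elsewhere. PP odds are p/(1 − f − p), so the odds ratio falls once f_P/f_A exceeds 0.94/0.84 = 1.12. At 5%/10% the difference rises while the odds ratio falls.

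**No ITT effect.** With ITT remission of 10% in both arms, TFR of 20%/5% gives 12.5% versus 10.5% in PP, and 5%/20% gives 10.5% versus 12.5%. The two-sided Fisher rejection rate goes from 4.23% to 8.56% and 9.45% respectively. A PP difference can thus arise from TFR rates alone, in either direction.

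**After the fix.** If TFR patients stay in PP as non-responders and nothing else is excluded, PP returns 16.0% versus 6.0% and 10.0 points at any TFR rate.

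**The case against.** The strongest defence is that the medication items in TFR are labelled protocol-prohibited, and SAP 5.2 defines PP as patients without a major deviation that could affect efficacy. On that reading the exclusion is conventional. This stands in part: a case for excluding those patients exists. But it does not remove the selection on outcome, since these patients are non-responders by rule whatever the deviation is called. Nor does it cover colectomy or ostomy, which Protocol 13.9 lists apart from prohibited medication.

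The second defence is containment, and it stands as a limit on severity. ITT is primary and counts TFR as failure. The sensitivity analyses are supportive and outside Type I error control. TFR is confirmed by blinded review, and the listing is finalised before unblinding. Blinding prevents choices that favour one arm; it does not stop the rule from deleting failures.

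A reader might go further and make any of three inferences.

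- *PP will shrink the effect and make a sound ITT result look fragile, because failures are commoner on placebo.* The documents give no TFR rate, the remission difference can grow even with twice the failures on placebo, and movements of a few tenths of a point do not show fragility.
- *SAP 10 contradicts SAP 5.2.* The visible list in 5.2 does not name TFR, but one item is redacted, so a contradiction cannot be asserted.
- *The effect on response can be sized from 57% versus 32%.* That pair appears only in Protocol Table 5, a precision table for totals of 30 to 150, and is not an adult Cohort 1 planning value.

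Rows of SAP Table 2 are redacted and SAP Appendix 1.3 is not visible, so an alternative TFR analysis may already exist.

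**Conclusion.** The point holds for the PP analyses of remission and response. SAP 10 conditions PP on outcome, inflates the rates in any arm with failures, and blurs what a PP-ITT difference means. Over the assumed TFR rates of 5% to 10% on active and 5% to 20% on placebo, the 10.0-point remission difference lies between 9.3 and 11.5 points. The size and sign depend on TFR rates that the documents do not give. The ITT primary analysis and the test hierarchy are untouched. It should be corrected because PP otherwise does not answer its stated question; it does not threaten the trial's main conclusion.

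**What to change.** Amend SAP 10 so that patients who meet TFR through UC-related events stay in PP and are counted as non-responders by NRI, the imputation Table 2 already names for PP. These events are the start or increase of corticosteroids or 5-ASA for UC, the start of an immunosuppressant or biologic for UC, and colectomy or ostomy. Prolonged corticosteroids or excluded medication for non-UC conditions remain PP exclusions under SAP 5.2. The amendment should say so explicitly, because prolonged non-UC corticosteroid use is also a TFR component and a blanket instruction to keep all TFR patients would clash with 5.2. Those remaining exclusions can still remove rule-based non-responders, but not for reasons driven by lack of effect.

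If the sponsor prefers the planned PP set, report it beside this version.

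The cost is SAP wording and one rerun of the PP analyses. The downside is that PP then contains some patients on prohibited UC medication, all counted as failures.

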11. SAFETY ANALYSIS

All analyses of safety data will be conducted using the Safety population by treatment/cohort and in Total RPC1063 1 mg unless specified otherwise. Individual data listings will also be provided. General conventions on data reporting and analysis regarding reporting formats, definitions of Baseline, change, percent change, analysis visit window, and treatment failure rules can be found in [Appendix 1](#). Analysis visits will be assigned for laboratory, vital signs, ECG, and pulmonary function test (PFT) data as per [Appendix 1.3](#).

No imputation of missing safety data will be performed except in the case of incomplete onset/stop dates for AEs, prior and concomitant medications ([Appendix 2](#)).

11.1. Adverse Events

AEs will be monitored during the trial and the data analyzed with respect to incidence within each treatment group as well as severity and potential relationship of the AEs to investigational drug.

A serious adverse event (SAE) is any untoward medical occurrence that at any dose results in death, is life-threatening, requires inpatient hospitalization or prolongation of existing inpatient hospitalization, results in persistent or significant disability/incapacity, is a congenital abnormality/birth defector is an important medical event that may not be immediately life-threatening or result in death or hospitalization but jeopardize the patient or may require intervention to prevent one of the other outcomes listed in the definition above.

A treatment-emergent adverse event (TEAE) is any AE that emerges during treatment having been absent pre-treatment, or worsens relative to the pre-treatment state, excluding those with onset after first MP dose.

An overall summary of TEAEs during IP will include the number and percentage of patients with

- ≥ 1 TEAE
- ≥ 1 Moderate or Severe TEAE
- ≥ 1 Severe TEAE
- ≥ 1 Possible, Probable or Related TEAE
- ≥ 1 Related TEAE
- ≥ 1 Serious TEAE
- ≥ 1 Possible, Probable or Related Serious TEAE
- ≥ 1 Related Serious TEAE

- ≥ 1 TEAE Leading to Discontinuation of Study Drug
- ≥ 1 TEAE Leading to Interruption of Study Drug
- Death
- Death Related to Study Drug

TEAEs will also be summarized and presented by decreasing frequency in the sort keys below in the Cohort 1 RPC1063 1 mg group:

- by system organ class and preferred term: all TEAEs, related TEAEs, severe TEAEs, serious TEAEs, possible, probable or related serious TEAEs, TEAEs leading to interruption of study drug, TEAEs leading to discontinuation of study drug
- by preferred term: all TEAEs, TEAEs with $\geq 2\%$ higher incidence rate in RPC 1 mg than placebo, TEAEs with incidence rate $\geq 5\%$, TEAEs with incidence rate $\geq 2\%$
- by system organ class, preferred term, and maximum severity: all TEAEs

Patients with multiple events reported for the same summary level will be counted only once.

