- It disappears or decreased on cessation or reduction in dose. There are exceptions when an AE does not disappear upon discontinuation of the drug (eg, bone marrow depression, fixed drug eruptions, tardive dyskinesia, etc.)
- It follows a known pattern of response to the suspected drug
- It reappears or worsens if the drug is re-administered

All efforts should be made to classify the AE according to the above categories.

After initiation of investigational drug, all AEs, regardless of relationship to investigational drug, will be recorded until the patient completes his or her last trial visit.

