12.2.5. Reporting of Serious Adverse Events

Reporting requirements for SAEs will be managed on behalf of the Sponsor by the CRO. Full details of the procedures to be adopted will be documented in a safety management plan approved by responsible parties, in brief:

The Investigator will report any SAE that occurs to any patient from the time written informed consent/assent is signed through the last visit. All SAEs that occur within 90 days of the last dose of treatment with the investigational drug, whether or not considered related to the investigational drug, must also be reported. Any SAE that is ongoing when the patient completes the trial or discontinues from the trial will be followed by the Investigator until the event has resolved, stabilized, or returned to Baseline status.

Any AE considered serious by the Investigator or Sub-investigator or that meets serious criteria should be reported to the CRO's Pharmacovigilance group using the designated SAE reporting forms and procedures. Data entry must be completed within 24 hours from the time the trial site personnel first learned of the event.

[REDACTED]

[REDACTED]

The initial report should be promptly followed by detailed, written reports, which will include copies of hospital case records, discharge summaries, autopsy reports, and other documents when requested and applicable. For unrelated cases, a full detailed case description may negate the need for additional hospital case records, discharge summaries, etc.

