13.4.3. Safety Analyses

All safety analyses will be carried out on the Safety population.

Adverse events will be monitored during the trial and the data analyzed with respect to incidence within each treatment group as well as severity and potential relationship of the AEs to investigational drug. Adverse events with onset on, or after the first dose of investigational drug or with onset prior to the first dose of investigational drug that increase in severity on, or after the first dose of investigational drug will be considered treatment-emergent. Treatment-emergent AEs will be summarized for the Safety population by System Organ Class and Preferred Term, and presented in descending order of frequency within each System Organ Class. Serious AEs and AEs leading to discontinuation will be summarized similarly.

Associated laboratory parameters such as hepatic profile, renal function, and hematology values will be grouped and presented together. For each laboratory test, individual patient values outside the standard reference range will be flagged and listed. Shift tables will be produced showing the frequency of shifts from Baseline to the lowest and to the highest on-trial value in and out of the normal range as well as by visit. Changes from Baseline to each visit for each laboratory parameter will also be summarized.

The change from Baseline to each visit for each of the vital sign variables will be summarized. Abnormal vital sign values will be flagged and listed.

The change from Baseline to each visit for each of the ECG parameters will be summarized. An outlier analysis of ECG results will be conducted.

The change from Baseline for each of the PFT parameters will be summarized. An outlier analysis of PFT results will be conducted.

OCT parameters will be summarized.

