Ozanimod causes a dose-dependent reduction in peripheral lymphocyte count because of reversible retention of lymphocytes in lymphoid tissues. In the controlled RMS trials, mean absolute lymphocyte counts during treatment with ozanimod were approximately 45% of baseline values. Ozanimod may therefore increase the susceptibility to infections. In the Phase 3 RMS program, 0.4% of subjects on 0.46 mg ozanimod and 3.3% of subjects on 0.92 mg ozanimod developed ALC below $0.2 \times 10^9/L$ with no distinct pattern of timing. An association between ALC $< 0.2 \times 10^9/L$ and serious or opportunistic infections was not detected; however, an increased risk of infection cannot be ruled out.

In active-controlled completed RMS clinical trials, the overall rate of infections (35%) with Ozanimod was similar to that of IFN β -1a. Ozanimod treatment was associated with a higher frequency of viral upper respiratory tract infections, urinary tract infections, and herpes zoster. The overall rate of serious infections was similar between ozanimod (1%) and IFN β -1a (0.8%) in active-controlled MS clinical trials (also refer to protocol [Section 6.2.5](#)).

Phase 2 UC and CD data follow a similar pattern.

After discontinuing ozanimod 0.92 mg, the median time to recovery of peripheral blood lymphocytes to the normal range was 30 days, with approximately 90% of subjects recovering within 90 days.

Vaccinations

No clinical data are available on the efficacy and safety of vaccinations, including live attenuated, in subjects taking ozanimod. The use of live attenuated vaccines is to be avoided during treatment with ozanimod and for 90 days after treatment discontinuation.

Pulmonary Effects:

Pulmonary function is known to be affected by fingolimod, a non-selective S1P receptor modulator, and increased collagen or fibrin deposition in the lung as has been reported in toxicology studies with fingolimod. In nonclinical studies, ozanimod did not induce smooth muscle hypertrophy, and no effect on respiratory function was observed with ozanimod administration in rodents. In patients with multiple sclerosis, the pulmonary data indicate that mild reductions in FEV1 and DLCO occurred early in treatment with ozanimod 1 mg but were not clinically meaningful and did not progress. Pulmonary effects are not considered to be a risk associated with ozanimod treatment.

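### SAP 11.1, read literally, leaves new adverse events after the last dose out of the TEAE and AESI tables, where Protocol 13.4.3 would count them

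*SAP*

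**What the plan says.** The SAP definition (11.1) has two limbs and one cut-off. The first limb reads: "A treatment-emergent adverse event (TEAE) is any AE that emerges during treatment having been absent pre-treatment". The second limb adds events that become worse than they were before treatment. The cut-off is given as "excluding those with onset after first MP dose". The first limb, for new events, is tied to treatment. The second limb, for worsening events, carries no time limit. The section does not say when treatment ends for this purpose.

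Protocol 13.4.3 starts from "Adverse events with onset on, or after the first dose of investigational drug" and adds pre-existing events "that increase in severity on, or after the first dose of investigational drug will be considered treatment-emergent". It gives no end date for either kind.

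Collection runs past the last dose. Protocol 12.2.4 says that "all AEs, regardless of relationship to investigational drug, will be recorded until the patient completes his or her last trial visit". Protocol 12.2.5 requires reporting of "All SAEs that occur within 90 days of the last dose of treatment with the investigational drug". Protocol 7.3.6 and 8.4 ask patients who stop drug to attend 30-day and 90-day follow-up visits.

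The tables in SAP 11.1 (overview, system organ class and preferred term, preferred term, maximum severity) are TEAE tables, and so is the special-interest table in SAP 11.2. Two death rows in the overview are not labelled as TEAEs. SAP 11.3 lists all deaths with treatment group and days from last dose, and SAP 11 promises individual listings.

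**The concern.** The two documents give different rules for the same event, and the readable part of the SAP gives no reason for the change. SAP 11.1 and 11.2 plan no by-arm table of all collected events beside the TEAE tables. An event that fails the TEAE definition therefore has no incidence comparison between arms.

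The period after stopping is not pharmacologically empty. For patients who stop the 0.92 mg dose, Protocol Appendix 3 reports that "the median time to recovery of peripheral blood lymphocytes to the normal range was 30 days, with approximately 90% of subjects recovering within 90 days". An infection a few weeks after the last dose is one that a safety reader would want to see by arm. SAP Section 2 also says that the results are meant as primary efficacy and safety data for a marketing application.

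**Working it through.** The plan states no figure that depends on this definition, so there is nothing to reproduce. The check sets the rules side by side and then does simple window arithmetic.

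**Which events differ**

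| Event in a patient who has stopped drug | Protocol 13.4.3 | SAP 11.1, read literally |
|---|---|---|
| New event after last dose, no MP or OLE entry | Counted | Not counted |
| Pre-existing event that worsens after last dose | Counted | Not clearly excluded (no time limit on this limb) |
| Death after last dose | Not separately addressed | Overview row not labelled TEAE; always in the 11.3 listing |
| Event after first MP dose | Counted, no period split | Excluded, properly: this SAP covers induction only |

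The conflict is confined to the first row.

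**Why the literal reading is the natural one.** For patients not entering the MP, SAP 9.1 measures treatment duration from first to last dose. SAP 11.4, 11.5, 11.8 and 11.9 treat the last on-treatment measurement as a category of its own. The MP cut-off closes the window for patients who go on dosing. It does not extend the window for those who stop.

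**Example.** A patient stops at Day 35, enters neither the MP nor the OLE, and has a serious infection 20 days later (Day 55). The event is inside the 90-day SAE period. Under the protocol it is a treatment-emergent serious event. Under the literal SAP wording it is missing from the serious-TEAE table and the AESI table and is seen only in a listing.

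**Share of one patient's collection window that is off drug**

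Inputs: induction of 10 weeks = 70 days (SAP 4.1); final follow-up visit at 90 ± 10 days after last dose (Protocol Table 1); stop at Day 35 (assumption).

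Share = follow-up days / (on-drug days + follow-up days)

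- Full course: 90 / (70 + 90) = 90/160 = 56%. Range: 80/150 = 53% to 100/170 = 59%.
- Stop at Day 35: 90 / (35 + 90) = 90/125 = 72%. Range: 80/115 = 70% to 100/135 = 74%.
- Straight into the MP or OLE: essentially 0%.

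These are shares of observation time for one patient who completes follow-up. They are not event counts.

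**Number of patients.** The documents do not give it. SAP 4.1 offers the OLE to adults who complete induction as non-responders, complete the MP, or relapse in it. Adults who stop early in induction are not named there, so they are the main group left in off-drug follow-up. The nearest planning figure is in Protocol 13.1: about 420 − 400 = 20 RPC1063 responders not entering the MP. It does not say how many of them are followed off drug, and it leaves out early stoppers.

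**The case against.** The strongest reply is that SAP 11.1 writes no last-dose cut-off. The phrase is undefined, the only explicit end point is the first MP dose, and SAP 9.1 defines exposure, not an event window. SAP Section 2 says the plan is to be read with the protocol, so Protocol 13.4.3 could supply the missing end date. This stands in part: the exclusion is the literal reading and not a stated rule. But reading the two together does not settle which governs when they differ. Two programmers could build different tables from the same text.

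Appendices 1 and 2 of the SAP are not in the text available and might define the window. SAP 11 cites them for reporting formats, baseline and change, visit windows, treatment failure rules and incomplete dates, and not for a TEAE window. The possibility remains open.

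A reader might also infer more than the documents support:

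- *That all by-arm AE output loses these events.* The two death rows and the worsening limb are not clearly limited.
- *That death reporting would suffer.* All deaths are listed with days from last dose in any case.
- *That the comparison would favour the drug.* The definition is the same in both arms, and no stopping rates by arm are given. Appendix 3 also says that no association between very low lymphocyte counts and serious or opportunistic infections was detected, although a raised risk could not be excluded.
- *That the loss can be sized for the trial.* That needs an assumed stopping rate and complete follow-up. Protocol 8.4 limits collection to SAE follow-up once consent is withdrawn.

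**Conclusion.** The point holds as a conflict between two definitions that should be resolved before the induction safety tables are produced. Followed literally, SAP 11.1 leaves new events after the last dose out of the TEAE and AESI tables that Protocol 13.4.3 would put them in. It applies to patients who stop in induction and enter neither the MP nor the OLE. For such a patient the uncounted share of the collection window is 56% after a full course and 72% after an assumed stop at Day 35, if the 90-day visit is completed. The number of events is unknown and no between-arm direction is shown.

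This rests on treatment ending at the last dose, as in SAP 9.1, and on the unseen appendices not defining the window otherwise.

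**What to change.** Replace the definition in SAP 11.1 with one that follows Protocol 13.4.3: onset, or increase in severity, on or after the first induction dose and before the first MP dose or first OLE dose; for patients who enter neither, through the last trial visit. The last trial visit matches the collection rule in Protocol 12.2.4 better than a fixed 90-day cap, which Protocol 13.4.3 does not contain. The MP and OLE limits only assign each event to the period in which it began.

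Flag events with onset after the last dose, so that on-treatment incidence can be shown beside the full figure.

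The cost is one sentence and one derived flag, on data that the protocol already collects. Reported incidences would rise slightly. Some added events would follow a change of therapy, because Protocol 8.4 allows alternative UC treatment after the 30-day visit; the flag lets a reader separate them. Since Cohort 1 is analysed after the last patient's Week 10 visit, the SAP should also say how follow-up events that arrive after that cut are added.
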